3.2.8 End of Study

Subjects who complete all visits up to and including the Week 52 visit will have completed the study. Subjects who discontinue early will be asked to return for an early withdrawal visit, where all safety assessments should be performed (Table 15-1). Subjects with any ongoing AEs at this visit will continue to be monitored as outlined in Section 9.1.5. After completion of this study, subjects will be asked to enroll in a 4-year extension study to evaluate the long-term (a total of 5 years after dosing) safety and efficacy of DTX301.

4 Subject Selection

Subjects will be assigned to study treatment only if they meet all of the inclusion criteria and none of the exclusion criteria.

4.1 Inclusion Criteria

Each subject must meet all of the following criteria at Screening to be enrolled in this study:

1. Willing and able to provide written informed consent.

Protocol: 301OTC01

2. Males and females ≥ 18 years of age with documented diagnosis of late-onset (defined as first manifestation of signs and symptoms at > 30 days of age) OTC deficiency, confirmed via enzymatic, biochemical, or molecular testing. This may include identification of a pathogenic mutation, via pedigree analysis, liver OTC activity that is $< 20\%$ of normal activity, or elevated urinary orotate ($> 20 \mu\text{mol}/\text{mmol}$ creatinine) after an allopurinol challenge test [[Tuchman 2008a](#)].
3. Documented history of ≥ 1 symptomatic hyperammonemia event with ammonia $\geq 100 \mu\text{mol}/\text{L}$.
4. Subject's OTC deficiency is stable as evidenced by either a) no clinical symptoms of hyperammonemia OR b) plasma ammonia level $< 100 \mu\text{mol}/\text{L}$ within the 4-week period preceding the Screening visit.
5. Subject's plasma ammonia level on Day 1 (predose) is $< 100 \mu\text{mol}/\text{L}$, for patients who historically maintain normal ammonia levels, and the subject is clinically stable; OR subject's plasma ammonia level on Day 1 (predose) is $< 200 \mu\text{mol}/\text{L}$, for patients who historically are not able to fully control ammonia levels with baseline management, and the subject is clinically stable. If the Day 1 (predose) ammonia level is inconsistent with the subject's clinical status, the ammonia level may be repeated to ensure accurate results.
6. On ongoing daily stable dose of ammonia scavenger therapy for ≥ 4 weeks.
7. No known allergic reaction to any component of DTX301.
8. Willing and able to comply with study procedures and requirements, including periodic inpatient hospitalizations, frequent blood draws, and urine collections over a 24-hour period.
9. Hematology and coagulation panel results are within the normal range or, if outside the normal range, deemed not clinically significant in the opinion of the investigator.
10. Males and all females of childbearing potential must be willing to use effective contraception at the time of administration of gene transfer and for the 52 weeks following administration of DTX301 to prevent the potential transmission of the AAV vector. For male subjects, appropriate contraceptive methods include the use of a condom with spermicide. For female subjects, appropriate contraceptive methods include the use of a condom with spermicide plus at least 1 of the following:
 - a. Oral contraceptives, other hormonal contraceptives (vaginal products, skin patches, or implanted or injectable products), or mechanical products such as an intrauterine device;
 - b. Use of a diaphragm or cervical/vault cap;

Protocol: 301OTC01

- c. Previous female sterilization (surgical bilateral oophorectomy [with or without hysterectomy] or tubal ligation) at least 6 weeks prior to DTX301 administration. In case of an oophorectomy alone, the reproductive status of the subject must have been confirmed by follow-up hormone level assessment.

NOTE: Abstinence is an acceptable form of birth control; however, appropriate contraception must be used if the subject becomes sexually active. Abstinence is defined as sexual inactivity consistent with the preferred and usual lifestyle of the subject. Periodic abstinence (calendar, symptothermal, post-ovulation methods), withdrawal (coitus interruptus), spermicides only, and lactational amenorrhea methods are not acceptable methods of contraception. A condom with spermicide is required to be used by all sexually active vasectomized males in the study in order to prevent potential transmission of the vector via seminal fluid.

NOTE: Females of childbearing potential are defined as all females physiologically capable of becoming pregnant, unless they are using highly effective methods of contraception during for the duration of the study.

Females are considered post-menopausal and not of childbearing potential if they have had 12 months of natural (spontaneous) amenorrhea with an appropriate clinical profile (eg, age appropriate, history of vasomotor symptoms) or have had surgical bilateral oophorectomy (with or without hysterectomy) or tubal ligation at least 6 weeks prior to enrollment. In the case of oophorectomy alone, only when the reproductive status of the woman has been confirmed by follow up hormone level assessment is she considered not of childbearing potential.

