| | 
in the study in order to prevent potential transmission of the vector via seminal fluid.
 
NOTE: Females of childbearing potential are defined as all females physiologically capable of becoming pregnant, unless they are using highly effective methods of contraception for the duration of the study.
 
Females are considered post-menopausal and not of childbearing potential if they have had 12 months of natural (spontaneous) amenorrhea with an appropriate clinical profile (eg, age appropriate, history of vasomotor symptoms) or have had surgical bilateral oophorectomy (with or without hysterectomy) or tubal ligation at least 6 weeks prior to enrollment. In the case of oophorectomy alone, only when the reproductive status of the woman has been confirmed by follow up hormone level assessment is she considered not of childbearing potential.
 
Exclusion Criteria:
 
Subjects meeting any of the following criteria at Screening will be excluded from the study:
 
 1. At Screening or Baseline (Day 0), plasma ammonia level $\geq 100 \mu\text{mol/L}$ for patients who historically maintain normal ammonia levels; OR plasma ammonia level $\geq 200 \mu\text{mol/L}$ for patients who historically are not able to fully control ammonia levels with baseline management; OR signs and symptoms of hyperammonemia, with documented elevated ammonia level, during the 4-week period preceding Day 0. If the ammonia level is inconsistent with the subject's clinical status, the ammonia level may be repeated to ensure accurate results. 2. Liver transplant, including hepatocyte cell therapy/transplant. 3. History of liver disease as evidenced by any of the following: portal hypertension, ascites, splenomegaly, esophageal varices, hepatic encephalopathy, or a liver biopsy with evidence of stage 3 fibrosis. 4. Significant hepatic inflammation or cirrhosis as evidenced by imaging or any of the following laboratory abnormalities: alanine aminotransferase (ALT) or aspartate aminotransferase (AST) > the upper limit of normal (ULN), total bilirubin > $1.5 \times \text{ULN}$, alkaline phosphatase > $2.5 \times \text{ULN}$. 5. Serum creatinine > 2.0 mg/dL. 6. Evidence of active hepatitis B virus (HBV) or hepatitis C virus (HCV) infection, documented by current use of antiviral therapy for HBV or HCV or by hepatitis B surface antigen (HBsAg) or HCV RNA positivity. NOTE: Subjects with a history of HCV infection must have documentation of 2 negative viral assays by polymerase chain reaction (PCR), collected at least 6 months apart, to be considered negative for HCV. Subjects with a history of HCV infection who test positive for HCV RNA at Screening can be rescreened once, after they have been treated and have documentation of at least 2 negative samples collected at least 6 months apart. 7. History of human immunodeficiency virus (HIV) infection AND any of the following: CD4^+ cell count < 350 cells/mm^3, change in antiretroviral |

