| | 
qualified study personnel will determine if the subject is eligible for the study. This will be accomplished by reviewing the inclusion and exclusion criteria and completing all of the screening assessments. Screening assessments may be performed on more than 1 day; all assessments must be completed and results available and reviewed prior to Day 0.
 
Screening Assessments: Demographic data; OTC and general medical history; prior medications, therapies, and procedures; use of ammonia scavengers; dietary protein restrictions; vital sign measurements; height and weight will be recorded. A 12-lead electrocardiogram (ECG) and a complete physical examination will be performed. Blood samples will be collected for HBV, HCV, and HIV status; serum pregnancy test (females of childbearing potential only); AAV8 neutralizing antibody testing; AAV8 binding antibody immunoglobulin G (IgG) testing, and clinical laboratory assessments (clinical chemistry, plasma ammonia [STAT sample], hematology, urinalysis, and coagulation panel). Adverse events and SAEs will be monitored after the subject has provided written informed consent.
 
Subjects will be administered [1-¹³C]sodium acetate orally. Blood samples for determination of ureagenesis will be collected, via an indwelling catheter, before dosing (time 0) and at approximately 0.5, 1, 1.5, 2, 3, and 4 hours after dosing with [1-¹³C]sodium acetate. During Screening, assessment of rate of ureagenesis may be repeated if discrepant with subject’s clinical status and severity.
 
Subjects participating in Cohort 4 (Dosing Process Optimization) will start the prophylactic corticosteroid regimen at least 5 days prior to dosing with DTX301. The subject must be assessed as clinically and metabolically stable, and intercurrent illnesses (eg, viral infection) or concomitant medications known to affects transaminases, be excluded. At any time after initiation of prophylactic corticosteroid regimen, additional assessments of plasma ammonia levels, amino acid profiles or any other biomarker to assess subject safety and clinical status may be performed, at the discretion of the investigator and as clinically indicated.
 
Day 0 – Baseline Measurements
 
Subjects will be admitted on Day 0 for the baseline determination of the following: plasma ammonia (AUC₀₋₂₄) and urinary orotic acid levels over 24 hours.
 
Prior to the determination of plasma ammonia AUC₀₋₂₄, blood samples will be collected for OTC genotyping, AAV8 neutralizing antibody testing, AAV8 binding antibody IgG testing, anti-OTC antibody testing, amino acid panel, and clinical laboratory assessments (clinical chemistry, plasma ammonia [STAT sample], hematology, urinalysis, and coagulation panel). Saliva, urine, and stool samples will be collected to provide a baseline for assessment of viral shedding. A urine pregnancy test will be performed on all female subjects of childbearing potential. An ECG and a targeted physical examination will be performed. Vital sign measurements and weight will be recorded. Adverse events and SAEs will be monitored; concomitant medications, therapies, and procedures, use of ammonia scavengers and dietary protein restrictions will be recorded.
 |

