12. History of a malignancy for which the subject has received treatment in the past 2 years except for prostate cancer treated with watchful waiting or surgically removed non-melanoma skin cancer.
13. Has a positive serum pregnancy test at Screening (females of childbearing potential only), a positive urine pregnancy test at Baseline (Day 0; females of childbearing potential only), or is nursing.
14. Has any other significant medical condition that the investigator feels would be a risk to the subject or would impede the study.

5 Screening and Randomization Procedures

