9.2 Procedures for Handling Special Situations

9.2.1 Pregnancy

A serum pregnancy test will be performed on all female study subjects of childbearing potential during Screening. A urine pregnancy test will be performed on all female study subjects of childbearing potential at each visit specified in the Schedule of Events ([Table 15-1](#)).

Protocol: 301OTC01

Pregnancy is not regarded as an AE unless there is a suspicion that a study drug may have interfered with the effectiveness of a contraceptive medication. Any pregnancy in a female study subject that occurs during study participation must be reported using the paper Pregnancy Report Form and fax it to PPD PVG (Table 9-1). To ensure subject safety, each pregnancy in a female study subject must be reported to PPD PVG Department (contact information in Section 9.1.2.2) within 2 weeks of learning of its occurrence.

The pregnancy in a female study subject must be followed up to determine outcome (including spontaneous miscarriage, elective termination, normal birth, or congenital abnormality) and status of mother and child, even if the subject discontinued from the study. Pregnancy complications and elective terminations for medical reasons should not be reported as an AE or SAE. Spontaneous miscarriages must be reported as an SAE. All neonatal deaths that occur within 28 days of birth should be reported as an SAE.

Any SAE occurring in association with a pregnancy in a female study subject brought to the investigator's attention after the subject has completed the study and considered by the investigator as possibly related to the study product, must be promptly reported to Ultragenyx Pharmaceutical.

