15.1 Appendix: Schedules of Events

Table 15-1 Schedule of Events – Outpatient, Home Health Services, and Inpatient Clinic Visits

| Procedure | Screening | Day 0 (Baseline) | Day 1 (DTX301 Dosing) | | Treatment Period: Includes Inpatient Clinic (shaded gray) and Outpatient Clinic/HHS visits. For home visits, refer to Table 15-2 . | | | | | | | | | End of Study/ Early Withdrawal | |
|---------------------------------------------------------------------|-----------|---------------------|--------------------------------|-------------------------------|----------------------------------------------------------------------------------------------------------------------------------------------------|------------|----------------|------------|----------------|------------|----------------------|----------------|------------|--------------------------------------|----|
| | | | Prior to DTX301 Infusion | DTX301 Dosing/ Postdose | OC/ HHS | OC/ HHS | IC | OC/ HHS | IC | OC/ HHS | OC (all subjects) | IC | OC/ HHS | | IC |
| Visit Type | OC | IC | | | | | | | | | | | | | |
| Week | – | – | – | – | 2 | 4 | 6 | 10 | 12 | 16 | 20 | 24 | 36 | 52 | |
| Day | –35 to –1 | 0 | 1 | 1 | 14 | 28 | 42 | 70 | 84 | 112 | 140 | 168 | 252 | 364 | |
| Visit Window (Days) | – | – | – | | ±2 | ±2 | ±2 | ±2 | ±2 | ±7 | ±7 | ±7 | ±7 | ±7 | |
| Informed consent | X | | | | | | | | | | | | | | |
| Eligibility criteria | X | | | | | | | | | | | | | | |
| Demographics | X | | | | | | | | | | | | | | |
| OTC medical history | X | | | | | | | | | | | | | | |
| Medical history | X | | | | | | | | | | | | | | |
| Prior medication / therapies / procedures | X | | | | | | | | | | | | | | |
| HBV, HCV, HIV status | X | | | | | | | | | | | | | | |
| Serum pregnancy test (females of childbearing potential only) | X | | | | | | | | | | | | | | |
| Clinic admission | | X ^a | X ^a | | | | X ^b | | X ^b | | | X ^b | | X ^b | |
| Vital signs (HR, BP, RR) | X | X | X | X ^d | X | X | X | X | X | X | X ^e | X | X | X | |
| Temperature ^f | X | | X | | | | X | | X | | X | X | | X | |
| Height | X | | | | | | | | | | | | | | |

| Procedure | Screening | Day 0 (Baseline) | Day 1 (DTX301 Dosing) | | Treatment Period: Includes Inpatient Clinic (shaded gray) and Outpatient Clinic/HHS visits. For home visits, refer to Table 15-2 . | | | | | | | | | | End of Study/ Early Withdrawal |

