|---------------------------------------------------------------------|-----------|---------------------|--------------------------------|-------------------------------|----------------------------------------------------------------------------------------------------------------------------------------------------|------------|----------------|------------|----------------|------------|----------------------|----------------|------------|----------------|--------------------------------------|
| | | | IC | | OC/ HHS | OC/ HHS | IC | OC/ HHS | IC | OC/ HHS | OC (all subjects) | IC | OC/ HHS | IC | |
| Visit Type | OC | IC | Prior to DTX301 Infusion | DTX301 Dosing/ Postdose | OC/ HHS | OC/ HHS | IC | OC/ HHS | IC | OC/ HHS | OC (all subjects) | IC | OC/ HHS | IC | |
| Week | - | - | - | - | 2 | 4 | 6 | 10 | 12 | 16 | 20 | 24 | 36 | 52 | |
| Day | -35 to -1 | 0 | 1 | 1 | 14 | 28 | 42 | 70 | 84 | 112 | 140 | 168 | 252 | 364 | |
| Visit Window (Days) | - | - | - | - | ±2 | ±2 | ±2 | ±2 | ±2 | ±7 | ±7 | ±7 | ±7 | ±7 | |
| Weight | X | X | | | | | | | | | | | | X | |
| Urine pregnancy test (females of childbearing potential only) | | X | | | X | X | X | X | X | X | X ^c | X | X | X | |
| Orotic acid spot urine | | | | | X | X | | X | | X | X ^c | | X | | |
| 24-hour urine orotic acid ^{g, h} | | X | | | | | X | | X | | | X | | X | |
| Sample for OTC genotyping | | X ^c | | | | | | | | | | | | | |
| Clinical chemistry (including LFTs) ⁱ | X | X ^c | X | X ^j | X | X | X ^c | X | X ^c | X | X ^c | X ^c | X | X ^c | |
| LFTs (STAT sample at local laboratory) ⁱ | X | X | X | X ^j | X | X | X | X | X | | | X | | X | |
| Spot ammonia (STAT sample at local laboratory) | X | X ^c | X | X ⁿ | X | X | X ^c | X | X ^c | X | X ^c | X ^c | X | X ^c | |
| Hematology / coagulation panel | X | X | | | X | | X | | X | | | X | | X | |
| Urinalysis | X | X | | | | | X | | X | | | X | | X | |

| Procedure | Screening | Day 0 (Baseline) | Day 1 (DTX301 Dosing) | | Treatment Period: Includes Inpatient Clinic (shaded gray) and Outpatient Clinic/HHS visits. For home visits, refer to Table 15-2. | | | | | | | | | | End of Study/ Early Withdrawal |

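### The definition of childbearing potential leaves out women on undefined highly effective contraception, so as written no pregnancy test is required for them, including before the gene transfer

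*Protocol*

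**What the plan says.** The definition stands in a note under inclusion criterion 10 in Protocol Section 4.1: "Females of childbearing potential are defined as all females physiologically capable of becoming pregnant, unless they are using highly effective methods of contraception". The synopsis has the same note, with the exception worded "unless they are using highly effective methods of contraception for the duration of the study". A further paragraph in both places classes post-menopausal and surgically sterilised women as not of childbearing potential.

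The pregnancy-test rules all refer to that definition:

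- Exclusion 13 (Section 4.2): "Has a positive serum pregnancy test at Screening (females of childbearing potential only), a positive urine pregnancy test at Baseline". The Day 0 urine test carries the same restriction, and nursing is also excluded.
- Section 9.2.1: "A urine pregnancy test will be performed on all female study subjects of childbearing potential at each visit" given in the schedule. The Screening serum test is limited in the same way.
- Synopsis, Day 0: "A urine pregnancy test will be performed on all female subjects of childbearing potential".
- Table 15-1: the rows begin "Serum pregnancy test (females of childbearing potential only" and "Urine pregnancy test (females of childbearing potential only". SAP Appendix B reproduces both.

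Criterion 10 itself asks for contraception that is effective or appropriate. For female subjects it lists a condom with spermicide plus at least one further method. Item (a) of that list is "Oral contraceptives, other hormonal contraceptives (vaginal products, skin patches, or implanted or injectable products), or mechanical products such as an intrauterine device".

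**The concern.** A pregnancy test before dosing exists to catch a pregnancy that nobody suspects, including one that occurs despite contraception. The definition takes the test away from a group of women because they use contraception. Section 9.2.1 itself allows that contraception may fail: it treats a pregnancy as an adverse event when the study drug is suspected of having interfered with a contraceptive.

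DTX301 is given once and cannot be withdrawn. The protocol's introduction (Section 1) lists the postpartum period and high-dose corticosteroids among the settings in which adults with late-onset disease have become hyperammonemic. Cohort 4 takes prednisone 60 mg/day from at least 5 days before dosing. A missed pregnancy would therefore matter for the woman as well as the fetus.

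**Working it through.** The plan gives no figure to reproduce. The check traces the definition through the text and then counts the tests that depend on it.

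**Step 1. Who is outside the definition?** Two groups: post-menopausal or surgically sterilised women, and fertile women using a highly effective method for the whole study. Only the second group can become pregnant.

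**Step 2. Does any rule test women outside the definition?**

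| Place | Who is tested |
|---|---|
| Exclusion 13 (Section 4.2 and synopsis) | Females of childbearing potential |
| Section 9.2.1, serum and urine | Females of childbearing potential |
| Synopsis, Screening and Day 0 | Females of childbearing potential |
| Table 15-1, both rows (and SAP Appendix B) | Females of childbearing potential |
| Rescreening (Section 3.2.1 and Table 15-1, Note 1) | Serum test only where applicable |

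No rule requires a test in all females or in all premenopausal females.

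**Step 3. Does another rule keep an untested pregnant woman out?** Exclusion 13 turns on a positive test or nursing. It has no separate exclusion for being pregnant, so a woman who is not tested cannot meet its pregnancy limb. Exclusion 14 is at the investigator's discretion and helps only if the pregnancy is known. Section 6.2.4 requires contraception, not testing. Section 9.2.1 requires any pregnancy to be reported and followed, which again presupposes that it has been detected.

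**Step 4. Can the exception be applied?** Three features prevent consistent use:

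- The term highly effective appears only in this note and is not defined. Criterion 10 uses different words.
- The exception depends on use throughout the study, while the two tests in exclusion 13 fall at Screening and Day 0. The condition lies in the future when it has to be judged.
- It is circular. Criterion 10 puts the contraception duty on females of childbearing potential and offers hormonal methods and intrauterine devices as ways to comply. If those methods count as highly effective, complying removes the woman from the group that has the duty.

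**Step 5. Count of tests, from Table 15-1.**

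- Serum: Screening = 1.
- Urine before dosing: Day 0 = 1.
- Urine after dosing: Weeks 2, 4, 6, 10, 12, 16, 20, 24, 36 and 52 = 10.
- Total = 1 + 1 + 10 = 12, of which 1 + 1 = 2 precede dosing and 10 follow it.

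**Step 6. Number of women.** With the term undefined, this cannot be derived. If no method qualifies, or no site accepts the condition as met, it is 0. If every fertile woman's method is accepted, it is every fertile woman among the up to 18 subjects.

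**The case against.** The best reply is that the exception defeats itself. If use for the whole study cannot be established before dosing, no woman can be shown to qualify by Day 0. The general rule, physiological capability, then applies and both pre-dose tests stay in force. Criterion 10(a) points the same way: it lists hormonal methods and intrauterine devices as ways in which women of childbearing potential comply, so the authors seem to regard users of those methods as still in the group. The sentence in Section 4.1 is also visibly garbled, which suggests a drafting slip, and the schedule shows a clear intention to test. Any exempted woman would be using good contraception, so the remaining risk is small.

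Some of this stands. Sites may well test anyway, nothing in the documents shows a missed test, and the sponsor probably did not mean to leave fertile women untested. It is fair to call the clause contradictory.

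It does not restore the requirement. A site that accepts a woman's stated intention to continue her method can treat her as exempt and remain within the text. The argument from criterion 10 is weak because item (c) of the same list names surgical sterilisation, and the following paragraph expressly puts sterilised women outside the definition. Being on the list therefore does not show that a woman is of childbearing potential. A safeguard before an irreversible infusion should not depend on sites choosing the more cautious of two readings.

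**Conclusion.** The concern holds. Followed as written, the protocol allows a fertile woman to receive DTX301 with no required pregnancy test, and no other provision fills the gap. The size is 12 tests per affected woman, 2 before and 10 after dosing, provided she is treated as exempt at every visit. The number of women lies between none and every fertile woman among the up to 18 subjects; the documents do not allow a narrower statement.

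The conclusion rests on the literal wording and makes no claim that a test was missed. SAP Section 3.1 reports that Cohort 4 enrolment closed after 2 patients. The pre-dose benefit of a correction therefore applies to any further dosing under this protocol and to any later protocol that reuses the definition. The contraception duty is not in question. This should be corrected.

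**What to change.** End the definition after the physiological criterion: delete the exception for users of highly effective contraception in Section 4.1 and the matching clause in the synopsis. Keep the paragraph on post-menopausal and surgically sterilised women, which then becomes the only route out of the group. If the sponsor wants to name preferred methods, they can be listed under criterion 10 without any link to testing.

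Exclusion 13, Section 9.2.1, Table 15-1 and the rescreening rules then work without further edits. The cost is one clause deleted in two places. No visit or procedure is added, because all 12 tests are already in the schedule.
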